### **2.5.1. Selection of dose and treatment schedule in the study**

The dose of reparixin proposed for this trial (2.772 mg/kg body weight/hour) is the same being administered in the ongoing clinical trials in islet allo-transplantation. It was originally derived from the effective reparixin concentrations found both in “in vitro” inhibition of CXCL8-induced chemotaxis of human PMN and in experiments in mouse models of syngeneic and allogeneic transplantation. Such a dose was found safe in previous phase 1 and 2 studies. Also, preliminary data obtained in the ongoing pilot trial in islet allo-transplantation confirm the efficacy and the safety of such a dose.

Consistent with experimental data in animals and preliminary data in the ongoing pilot trial in islet allo-transplantation, the proposed schedule of administration (continuous infusion for 7 days) is intended to expose the patient to reparixin throughout the time-window of relevant inflammatory post-transplant events after both allo-transplantation and IAT [Pollard, 2011; Citro, 2011].

### **2.5.2. Alternative treatments**

There are no specific pharmacologic treatments addressed to the prevention of graft failure after IAT. A trial is currently ongoing to test the potential effect of sitagliptin in IAT (NCT01186562). Because of this, patients not willing to participate in the study may either be offered to participate in another trial of experimental treatment or will not be offered any specific alternative treatment.

All patients, regardless of study participation, will receive the standard of optimal care for the transplanted organ (procurement, storage, isolation, infusion) and the recipient.

### **2.5.3. Risk - benefit evaluation**

#### **2.5.3.1. General risks**

Transplantation of islets is associated with several potential risks. These are intrinsic to the procedure and may result from the intra-hepatic islet infusion as well as testing involved in the care and evaluation of transplanted subjects. All patients receiving IAT are at risk of complication regardless of study participation.

Administration via a high flow central vein, which was proven to be safe in lung and kidney recipients, as well as in patients undergoing islet transplant, is proposed for the study to minimize the risk of infusion-site toxicity seen in a cohort of volunteers receiving i.v. infusion via a peripheral vein.

#### 2.5.3.3. Central line

The study drug will be administered as a continuous i.v. infusion over 7 days with a catheter inserted in a (high flow) central vein. The risks of a central line are not considered study-related risks since a central line is routinely placed in patients undergoing post-pancreatectomy IAT for their routine clinical care. This required access will be maintained for a period of time that might be slightly longer than that routinely used. Nevertheless, central line care as routinely practiced by the participating sites will minimize the risk of thrombosis and infections.

#### 2.5.3.4. Blood sampling

In addition to the routine blood sampling, participation in the study will require an amount of blood slightly higher than routine sampling at some time points (not exceeding 5mL at each time point), to allow study specific measurements and centralized assay of C-peptide, HbA1c, inflammatory chemokines/cytokines, miR-375 and PK samples.

#### 2.5.3.5. Other study related procedures

No other procedures specifically associated to the study are required. Type, timing and frequency of some measurements, e.g. stimulation test by a Mixed Meal Tolerance Test (MMTT), might be guided by the protocol, but such measurements are basically part of standard patient care and would be performed regardless of study participation.

2.5.3.6. Potential benefit

To the patients: According to preliminary data obtained in islet allo-transplantation, patients receiving reparixin are likely to benefit with improved auto-graft function, but this is to be confirmed. Patients assigned to the control arm are expected to obtain no additional benefit other than that established in IAT recipients.

To society: This study may identify a useful medication that will make post-pancreatectomy IAT more effective for future recipients.

### **3. OVERALL STUDY DESIGN AND PLAN DESCRIPTION**

#### **3.1. STUDY DESIGN**

The study will be a phase 2/3, multicenter (US), randomized, double-blind, placebo-controlled, parallel assignment pilot study.

The goal of this study is to reach a total of 100 adult patients who are randomized and receive IAT after total or completion pancreatectomy. Patients will be randomly (1:1) assigned to receive either reparixin [continuous i.v. infusion for 7 days (168hrs)], or matched placebo (control group), starting approximately 12hrs before islet infusion. The two groups will be balanced within each centre. All patients who are randomized and receive the Investigational Product (either reparixin or placebo) will be included in the ITT analysis. Patients will be in the ITT analysis whether or not they receive IAT, because exclusions cannot be made for events occurring after randomization that could be influenced by the randomized assignment.

Recruitment will be competitive among the study sites, until the planned number of patients is enrolled. Competitive recruitment has been chosen to increase the speed of recruitment and to account for any difference in transplant rate among study sites. Each centre will enroll patients as rapidly as possible, up to a maximum of 40 patients (as per the randomization list). A maximum of 48 patients is allowed for the site of the Primary Investigator. Each patient will be involved in the study for 7 day hospital stay during pancreatectomy followed by islet transplantation, for all required measurements up to hospital discharge and for 2 post-transplant visits scheduled @ day  $75\pm 14$  and  $365\pm 14$  after the transplant.

#### **3.2. STUDY TIME TABLE**

The planned patients are expected to be recruited in a 12 month period. A follow-up of 12 months is planned for each patient. Overall study timelines are reported below.

- Projected starting date (first-patient-in): December 2013
- Projected completion of patient accrual (last-patient-in): March 2015
- Projected study end date (last-patient-last-visit): March 2016

#### **3.3. END OF STUDY**

For the purpose of this trial, the end of study is defined as the date of the last visit of the last patient.

## 4. OBJECTIVES AND ENDPOINTS

### 4.1. STUDY OBJECTIVES

The objective of this clinical trial is to assess whether reparixin leads to improved transplant outcome as measured by the proportion of insulin-independent patients following IAT. The safety of reparixin in the specific clinical setting will be also evaluated

### 4.2. STUDY ENDPOINTS

#### 4.2.1. Primary efficacy endpoint

- The proportion of insulin-independent patients following IAT [time frame: day 365±14 after the transplant].

For the purpose of this protocol, insulin-independence is defined as freedom from the need to take exogenous insulin for 14 or more consecutive days, with adequate glycemic control, as defined by:

- a glycated hemoglobin (HbA1c) level  $\leq 6.5\%$ ;
- fingerstick fasting blood glucose not exceeding 126 mg/dL more than three times in the past week (based on a minimum of one daily measurement);
- a 2 hour post-prandial blood glucose not exceeding 180 mg/dL more than four times in the past week (based on a minimum of one daily measurement);
- a laboratory fasting glucose in the non-diabetic range ( $<126$  mg/dL).

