#### **6.5. CONCOMITANT THERAPY**

Any medications required for the patient's welfare are permitted and will be given at the discretion of the Investigator, except for drugs described in paragraphs below.

Administration of all prior (4 weeks prior to enrolment) and concomitant medications (CMEDs), apart from the agents listed below, during hospital stay will be reported in the appropriate section of the CRF. Only medications used for SAE, oral hypoglycemic drugs as well as medications that should not be used (see Section 6.5.1 below) will be reported after hospital discharge.

All the details as per the CRF fields (sequential number, drug name, indication, starting dose, start/stop date, route of administration) will be recorded. Change in dose will not be tracked.

The following agents do not need to be recorded:

Saline and other hydration solutions (including additional electrolytes)  
Total parenteral nutrition and enteral feeds  
Homeopathic medications  
Elective vitamins and minerals  
Topical agents with no or negligible systemic absorption  
Osmotic laxatives and locally acting antacids

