### **6.5.1. Other treatments**

Drugs required during surgery will be administered as per centre practice.

The following prophylactic anticoagulation is suggested to be used in patients enrolled in this study

- Heparin will be administered at a dose of 70 U/kg, divided equally between the islet bags, followed by 3 U/kg/hour infused i.v. for the next 4 hours. From the 5th to the 48th hour post-transplant, heparin will be titrated to achieve and maintain PTT in the range 50-60 seconds. Comparable marker other than PTT will be used as per site experience.
- Enoxaparin will be administered at a dose of 30 mg subcutaneously from day 2 to 7 post-transplant.

Prophylactic anticoagulation management (choice of medication and/or doses) might be adjusted on the basis of clinical requirements (e.g. occurrence of bleeding) and/or centre practice. Low Molecular Weight Sulfate Dextran cannot be used in this trial.

Glycemic control in the early post-transplant period will be achieved by insulin administration to target glucose levels in the range 80-180mg/dL. Patients will be tested for blood sugar by fingerstick a minimum of 4 times per day. Insulin will be titrated to maintain fasting and pre-meal blood sugars in the range 80-125 mg/dL, and 2 hour post-prandial glucoses <180 mg/dL. For patients on continuous enteral or parenteral feeds, insulin will be titrated to maintain glucose in the range 80-140 mg/dL.

The following medications should not be used in this study:

- Systemic steroids (i.e. intravenous, intramuscular, oral; intra-articular injection allowed): from 2 weeks prior to enrolment up to the end of the study; use of  $\leq 5$ mg prednisone daily or equivalent dose of hydrocortisone, for physiological replacement only is allowed.
- Any investigational agents: from 4 weeks prior to enrolment up to the end of the study;
- Any anti-cytokine/chemokine medications (e.g. anti-TNF $\alpha$ ): from 4 weeks prior to enrolment up to the end of the study;
- Any immune modulators: from 4 weeks prior to enrolment up to the end of the study;
- Low Molecular Weight Sulfate Dextran;
- Oral hypoglycemic agents and any drugs that influence insulin sensitivity.

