## 4 STUDY VARIABLES

### 4.1 Primary Variable

The proportion of insulin-independent patients at Day  $365 \pm 14$  days following IAT.

REP0112

Statistical Analysis Plan

For the purpose of this protocol, insulin-independence is defined as freedom from the need to take exogenous insulin for 14 or more consecutive days, with adequate glycemic control, as defined by:

- a glycated hemoglobin (HbA1c) level  $\leq 6.5\%$ ;
- fingerstick fasting blood glucose not exceeding 126 mg/dL more than three times in the past week (based on a minimum of one daily measurement);
- a 2 hour post-prandial blood glucose not exceeding 180 mg/dL more than four times in the past week (based on a minimum of one daily measurement);
- a laboratory fasting glucose in the non-diabetic range ( $<126$  mg/dL).

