## 6 ANALYSIS POPULATIONS

Five analysis populations will be identified and used in the summarization and analysis of data, namely all screened patients, all randomized patients, intent to treat, per protocol, and safety.

- All Screened Patients: This population will include all patients screened for participation in the trial.
- All Randomized Patients: This population will include all patients randomized to investigational product in the trial.
- Intent to Treat: This population will consist of all patients who are randomized and receive the investigational product (either reparixin or placebo). Summarization and analysis of this population will be based on randomized treatment, regardless of treatment actually received. Eligible patients will be included in this population whether or not they receive IAT, because exclusions cannot be made for events occurring after randomization that could be influenced by the randomized assignment.
- Per Protocol: This population will consist of all patients in the ITT population who meet all of the following criteria:
  - Received IAT
  - Completed 7 days of investigational product dosing
  - No major protocol violations, including violations of inclusion/exclusion criteria, errors in treatment assignment, use of prohibited medication, etc.
  - Visits occurring on Day 75 ± 14 days from IAT and Day 365 ± 14 days from IAT
  - Insulin-independence status recorded at Day 365 ± 14 days from IAT

Further criteria for exclusion from the PP population may be identified during the data review meeting held prior to database lock.

- Safety: This population will consist of all randomized patients. Summarization and analysis of this population will be based on treatment actually received.

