The treatment effect ( $\beta_{\text{treatment}}$ ) will be declared significantly greater than 0 at the 0.025  $\alpha$ -level. A model parameter estimate and the corresponding standard error, p-value, and odds ratio with a one-sided 95% confidence interval will be presented for the treatment effect.

The logistic regression sensitivity analysis will also be performed for the ITT population, dropping from the analysis any site with >20% of subjects not having the primary endpoint recorded, using the same approach used for the sensitivity analysis of the primary endpoint.

As further sensitivity analysis, the primary endpoint analysis and the corresponding logistic regression analysis will be repeated including Site 01 only, which is the largest site with the greatest number of patients receiving IAT, having possibly the best treatment balance, having a high rate of primary endpoint data capture, and also being the site with the highest experience in the field and thus transplanting patients under highly reproducible surgical and clinical conditions. When performing the logistic regression analysis, site will no longer be considered a covariate in the model. The intent of these analyses is to examine the sensitivity of the primary analysis to the low enrollment/treatment balance, lesser experience level, and lower rates of retention which may be present at the other sites.

For both the primary and sensitivity analyses, patients who die or who discontinue before the primary endpoint assessment at Day 365  $\pm$  14 days after IAT, or those who reach the Day 365 visit but have no primary endpoint assessment, will be treated as primary endpoint failures.

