Notes: Plots for mean values  $\pm$  standard error bars will be presented for each treatment group at each time point (where “Basal” is the single baseline which is the average of the two basal values). Each treatment group will be in a different color with an accompanying legend. Separate pages will be created for CXCL8 (pg/mL), CCL2 (MCP-1) (pg/mL), CCL3 (pg/mL), CCL4 (pg/mL), CXCL10 (IP-10) (pg/mL), CXCL9 (MIG) (pg/mL), IL-6 (pg/mL), IL-10 (pg/mL), INF- $\gamma$  (pg/mL), TNF- $\alpha$  (pg/mL), and IL-1 $\beta$  (pg/mL).

Dompé farmaceutici S.p.A  
Protocol REP0112

Page X of Y

Figure 14.4.15.1 miR-375, Plots of Mean Values Over Time – Safety Population

X-axis: Time Point (Pre-transplant 1, 6 Hours Post, 12 Hours Post, 24 Hours Post, 72 Hours Post, 120 Hours Post, and 168 Hours Post)

Y-axis: miR-375 (copies/mL), mean  $\pm$  standard error

Reference: 14.3.13, 16.2.15

Notes: Plots for mean values  $\pm$  standard error will be presented for each treatment group at each time point. Each treatment group will be in a different color with an accompanying legend.

Dompé farmaceutici S.p.A  
Protocol REP0112

Page X of Y

Listing 16.2.6.1.1 Insulin Independence, Alternative Definition

Treatment: Reparixin or Placebo

Patient Number	Visit	Date (Day) of Visit	Insulin Ind, Alternative Definition
XXXX	Day 365	DDMMMYYYY (XXX)	Yes
XXXX	Day 365	DDMMMYYYY (XXX)	Yes
XXXX	Day 365	DDMMMYYYY (XXX)	Yes
.	.	.	.
.	.	.	.
.	.	.	.

Reference: CRF Page 24 and 24.1 and listings 16.2.6.2, 16.2.6.3.1 and 16.2.6.4.

Notes: Ind = Independent. Alternative definition: freedom from the need to take exogenous insulin for 14 or more consecutive days; a glycated hemoglobin (HbA1c) level  $\leq$  6.5%; a laboratory fasting glucose in the non-diabetic range ( $<126$  mg/dL); and a 90 minute blood glucose not exceeding 180 mg/dL from the MMTT. This measure is proposed as an alternative to finger-stick 2-hour post-prandial glucose on patient diary.

Dompé farmaceutici S.p.A  
Protocol REP0112

Page X of Y

Listing 16.2.6.3 Mixed Meal Tolerance Test, C-peptide Area Under the Curve (AUC), Alternative Computation

Treatment: Reparixin or Placebo								
Patient Number	IEQ/kg Infused During IAT	Visit	Mixed Meal Administration Date (Day)	End Time	Time Point	Sample Time	C-peptide (ng/mL)	Area Under the Curve (unit)
XXXX	XXXXX	Day XXX	DDMMMYYYY (XXX)	HH:MM	Basal 1	HH:MM	X.XX	XXX.X
					Basal 2	HH:MM	X.XX	
					Basal	HH:MM	X.XX	
					15 min	HH:MM	X.XX	
					30 min	HH:MM	X.XX	

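### An ITT patient who is off insulin while taking a prohibited oral glucose-lowering drug can count as insulin-independent; the plan has no rule for this, and its size and direction by arm are unknown

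*Protocol*

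**What the plan says.** **Definition.** Protocol 4.2.1 states that "insulin-independence is defined as freedom from the need to take exogenous insulin for 14 or more consecutive days, with adequate glycemic control". Control then means HbA1c of at most 6.5%, limits on fasting and post-prandial fingerstick readings, and a laboratory fasting glucose below 126 mg/dL. SAP 4.1 repeats this. Neither text mentions glucose-lowering drugs other than insulin.

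**Status of those drugs.** Protocol 6.5.1 lists "Oral hypoglycemic agents and any drugs that influence insulin sensitivity" among medications that should not be used. Protocol 6.5 limits what is reported after discharge: "Only medications used for SAE, oral hypoglycemic drugs as well as medications that should not be used". The CRF fields include drug name and start and stop dates.

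**Primary analysis.** SAP 6 defines ITT as everyone randomized who receives investigational product, with no exclusion for prohibited drugs. SAP 7.5.1 counts as failures "patients who die or who discontinue before the primary endpoint assessment at Day 365", together with patients who reach that visit without an assessment. Prohibited drug use is not on the list.

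**Per-protocol set.** SAP 6 requires "No major protocol violations, including violations of inclusion/exclusion criteria, errors in treatment assignment, use of prohibited medication, etc". SAP 7.5 calls this analysis secondary and confirmatory; Protocol 9.4.2 calls it a sensitivity analysis.

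**Sensitivity analyses.** The others in SAP 7.5.1 concern sites with missing data, Site 01 alone, and site effects. The addendum's note to Listing 16.2.6.1.1 begins "Alternative definition: freedom from the need to take exogenous insulin for 14 or more consecutive days" and changes the glucose criteria, again with no clause on other drugs. Addendum section 3.2.1, on the primary variable, was not in the text available for this review and could not be checked.

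**The concern.** The endpoint is meant to show that the transplanted islets suffice without insulin. A patient who replaces insulin with another glucose-lowering drug may meet every criterion without showing that. The plan already fails patients who die, leave or are not assessed, and it collects the data needed to identify these users, but the primary analysis makes no use of that record.

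Two things are at stake. If would-be failures in both arms become successes at similar rates, the treatment difference shrinks and power falls. If conversion differs by arm, the estimate is biased in whichever direction that difference points. In addition, Protocol 7.2 has insulin-independence status assessed at the visit, so with no written rule two sites could classify the same patient differently.

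**Working it through.** **Inputs (Protocol 9.1).** Success on placebo and reparixin by islet-yield stratum: 13% and 40% (<2500 IEQ/kg), 23% and 55% (2500-5000), 55% and 84% (>5000). Stratum mix 34/42/24 from the 2006-2011 series. One-sided alpha 0.025, 1:1 allocation, 100 transplanted patients.

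**Step 1: the plan's own figure.** For 44 per arm, 23% v 55%, mean rate 0.39:

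power = Φ{[0.32 − 1.96·√(2·0.39·0.61/44)] / √[(0.23·0.77 + 0.55·0.45)/44]} = Φ[(0.320 − 0.204)/0.0982] = Φ(1.18) = 88.2%.

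The unpooled form gives 90.3% and exact enumeration 88.8%. The stated 90%, or 87% to 90% allowing for discreteness, is reproduced.

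**Step 2: stratified test at N=100.** Patients per arm by stratum, m = 17, 21, 12. Let D = Σ(m/2)(pT − pC), V0 = Σ(m/2)·p̄(1 − p̄), V1 = Σ(m/4)[pC(1 − pC) + pT(1 − pT)]. Power = Φ[(D − 1.96√V0)/√V1].

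- D = 8.5·0.27 + 10.5·0.32 + 6·0.29 = 7.395
- V0 = 5.425, V1 = 4.876
- Power = Φ[(7.395 − 4.565)/2.208] = Φ(1.28) = 90.0%

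**Step 3: conversion (assumed; the documents give no rate).** If a share f of would-be failures becomes successes, p becomes p + f(1 − p). With equal f the difference shrinks by the factor (1 − f). At f = 10% the middle stratum goes from 23% v 55% to 30.7% v 59.5%, and 32 points become 28.8. D = 0.9·7.395 = 6.656, V0 = 5.698, V1 = 5.253, so power = Φ(0.86) = 80.6%.

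| Converted, reparixin / placebo | Middle-stratum difference (points) | Power, formula | Power, simulated |
|---|---|---|---|
| none | 32.0 | 90.0% | 90% |
| 2% / 2% | 31.4 | 88.3% | 88% |
| 5% / 5% | 30.4 | 85.6% | 85% |
| 10% / 10% | 28.8 | 80.6% | 80% |
| 5% / 10% | 26.6 | 73.7% | 73% |
| 5% / 15% | 22.7 | 58.9% | 58% |
| 10% / 5% | 32.7 | 90.2% | 89-90% |
| 15% / 5% | 34.9 | 93.7% | 93% |

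**Step 4: type I error.** Let both arms have the placebo rates. With equal conversion D stays 0 and the one-sided error stays at 2.5%. With 15% on reparixin and 5% on placebo, the stratum differences are 0.10·(1 − p) = 0.087, 0.077, 0.045:

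- D = 8.5·0.087 + 10.5·0.077 + 6·0.045 = 1.818
- V0 = 5.124, V1 = 5.089
- Rejection rate = Φ[(1.818 − 4.437)/2.256] = Φ(−1.16) = 12.3%, and about 12% by simulation

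**Step 5: is the direction fixed?** In the middle stratum placebo gains 0.77·fC and reparixin 0.45·fT, so placebo gains more only while fT/fC < 0.77/0.45 = 1.71. Under a different assumption, where the drug shifts every patient by a fixed 0.3 SD across a normal threshold, 23% becomes 33.0% and 55% becomes 66.5%. Placebo then gains 10.0 points, reparixin 11.5, and power at 44 per arm is 89.4%. No direction follows without an assumption about who uses the drugs.

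**The case against.** Several points on the other side carry weight.

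- **Direction.** A reader might infer that the gap inflates placebo most, because placebo has more failures to convert. The documents say nothing about use by arm, and Step 5 shows that the direction depends on the conversion model. That reading is not supported.
- **Frequency.** A reader might infer from the recording requirement that use is expected. Protocol 6.5 records these drugs together with all other medications that should not be used; recording a breach does not show that it is common. Conversion also requires all four glycaemic criteria, so rates of 10% to 15% of failures are strong assumptions, and the 58% power case has no basis in the documents.
- **Baseline.** The planning rates come from a published series, and the plan does not say whether they exclude users of other drugs. If they include them, part of the apparent loss is already in the plan.
- **Partial handling.** The per-protocol analysis removes prohibited-drug users, SAP 7.4.2 tabulates by arm the deviations that exclude patients from it, and SAP 7.4.6 tabulates concomitant drugs by class. An imbalance could be seen. But that set also drops patients for no transplant, incomplete dosing and visits out of window, and removing a patient is not the same as counting a failure.
- **Choice of estimand.** Counting users by observed outcome is a recognised ITT approach, the stated objective is insulin independence, and C-peptide and β-score measure graft function separately. This makes it a design choice, but one the plan should state.

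The absence of any rule in the primary analysis survives all of these.

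**Conclusion.** The point holds in a limited form. As written, an ITT patient who is off insulin on a prohibited glucose-lowering drug and meets the criteria is a primary success, and no visible primary-endpoint sensitivity analysis in ITT addresses this.

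The size is a range under assumption. Equal conversion of 2% to 10% of would-be failures costs about 2 to 10 points of power. Placebo-heavy conversion costs more, to about 73% or 58% in the two cases shown. Reparixin-heavy conversion leaves power unchanged or raises it, and can favour the drug falsely. All figures assume that the planning rates describe independence without other glucose-lowering drugs.

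Equal use is not a validity problem, since type I error stays nominal. Because bias is possible in either direction and the data are already collected, the rule should be prespecified. This is a worthwhile improvement, not a fatal flaw.

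**What to change.** Before unblinding, add to SAP 4.1 and 7.5.1: patients with a recorded oral hypoglycaemic or other prohibited glucose-lowering drug in the 14 days before the Day 365 assessment are classed as not insulin-independent in the ITT analysis. Report the current definition as a sensitivity analysis. At minimum, prespecify the failure classification as an ITT sensitivity analysis and tabulate such use by arm.

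**Cost.** No new data are needed, since drug names and dates are CRF fields, and every patient stays in ITT. Because the definition sits in Protocol 4.2.1, a matching amendment may be required. Success rates will be slightly lower, and some users who would be independent without the drug will be classed as failures. A 14-day look-back also misses a drug stopped just before the window that may still influence HbA1c; the SAP should acknowledge that limit.

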## 7.2. FOLLOW-UP PROCEDURES AND ASSESSMENTS

Since hospital discharge, patients will self monitor glucose levels and insulin intake according to standard clinical instructions at the site. Insulin will be administered to target fasting and pre-meal glucose levels in the range 80-125 mg/dL, and 2 hour post-prandial glucoses <180 mg/dL. For patients on continuous enteral or parental feeds, insulin will be titrated to maintain glucose in the range 80-140 mg/dL.

The Investigator will identify if- and the date when- it is appropriate for the patient to stop insulin intake, according to standard of centre practice. Regardless the patient is on or off insulin, he/she will report on a Diary Card (see **Appendix 14.7**) his/her self monitored glucose levels for 14 consecutive days prior to the follow-up visits on day  $75 \pm 14$  and  $365 \pm 14$  after the transplant: glucose levels will be measured at least two times a day: 1) after an overnight fast (or anyway before breakfast if the patient is still on a tube feed and TPN); 2) within 2 hours post-prandial. Also, patients still on insulin will report on the Diary Card their daily insulin intake.

Patients will attend the centre for study assessments on 2 follow-up visits scheduled on day  $75 \pm 14$  and  $365 \pm 14$  after the transplant.

At each **visit**, the following will be evaluated/measured in all patients as per centre practice, unless otherwise specified. Measurements, including the actual date and time of assessment, or the date of sampling, will be recorded in the CRF.

- Patient weight.
- Retrospective self-measured glucose and insulin requirement data in the 2 weeks prior to the visit will be reviewed and average (previous week) insulin requirement at each time point as well as insulin-independence / insulin-dependence status will be assessed.
- Retrospective episodes of severe hypoglycaemia in the interval will be assessed as per centre practice. Events of documented hypoglycemia in the interval will be obtained from review of the patient's home glucometer download from between visits and/or patient glucose logs.
- Retrospective severity of steatorrhea in the 4 weeks prior to the visit will be evaluated.
- A blood sample will be taken prior to the meal administration to measure HbA1c, albumin and pre-albumin. ALT/AST will be also measured on day  $75 \pm 5$ .

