### **11.3. DATA MANAGEMENT**

Data management of the CRFs and Diary Cards will be performed by the CRO appointed by Dompé.

The CRF and Diary Card pages for all patients will be data-entered (double data entry) into the study database, and the data will be verified for missing data, inconsistencies, and for any necessary medical clarifications. Queries arising from these checks will be sent to the Investigator for response and signature.

Once all data queries have been resolved, the study will be declared to be "clean", and the study data will be locked ready for analysis.

After the database lock has been achieved, the Investigator may archive the copies of the CRFs and Diary Card retained at the centre. The original CRF and Diary Card collected by the CRO appointed by Dompé will be transferred to Dompé for archiving.

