#### 14.7. APPENDIX 7 – SAMPLE DIARY CARD

Clinical Trial REP0112	PATIENT DIARY CARD						PATIENT No.    
Sponsor: Dompé s.p.a.							

Please report in the table below your blood glucose (fingerstick) for 14 days before the planned follow-up visit. You are required to report at least one value taken after an overnight fast (or anyway before breakfast) and one value taken within 2 hours after one of the two meals. Also, please report the total amount of insulin you have taken each day.
 
Please add the date as day/month/year (example 25/07/2012 for 25 July 2012) and the time as 24 hours clock (example 9.35 in the morning, 21.35 in the afternoon). Please enter the information requested with indelible ink.
							
Day	Breakfast glucose		Lunch glucose		Dinner glucose		Daily Insulin
	Time	Value Before	Time	Value After	Time	Value After	
Monday - date:							
Tuesday - date:							
Wednesday - date:							
Thursday - date:							
Friday - date:							
Saturday - date:							
Sunday - date:							

Investigator's signature: \_\_\_\_\_ date: \_\_\_\_\_

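### Does a fixed cap of four high post-prandial readings, with no cap on the number of readings, undermine the primary endpoint?

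*Protocol*

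**What the plan says.** Protocol 4.2.1 defines insulin independence as at least 14 consecutive days without exogenous insulin plus four glycemic conditions. One is the post-prandial condition, a 2-hour value "not exceeding 180 mg/dL more than four times in the past week (based on a minimum of one daily measurement"). SAP 4.1 repeats it: "a 2 hour post-prandial blood glucose not exceeding 180 mg/dL more than four times in the past week".

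Protocol 7.2 sets a minimum for recording in the 14 days before each visit: "glucose levels will be measured at least two times a day", the first fasting and the second described as "2) within 2 hours post-prandial". The sample diary card (Appendix 14.7) asks for "one value taken within 2 hours after one of the two meals", but prints an after-meal column for both lunch and dinner.

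The classification is made at the site. Under Protocol 7.2 the self-measured data are reviewed at the visit and "insulin-independence / insulin-dependence status will be assessed". The SAP works from that result: a criterion for the per-protocol population in section 6 is "Insulin-independence status recorded at Day 365 ± 14 days from IAT", and SAP 7.5.1 counts as failures patients who reach Day 365 without an endpoint assessment. The diary itself is also captured (Protocol 11.3): "The CRF and Diary Card pages for all patients will be data-entered (double data entry) into the study database".

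The SAP addendum lists an alternative definition (note to Listing 16.2.6.1.1) that uses laboratory fasting glucose and the 90-minute glucose from the meal test, with no fingerstick values. Addendum 3.1 makes the endpoints it adds exploratory. Addendum section 3.2.1, on the primary variable, could not be read for this review.

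**The concern.** A fixed count over a variable number of readings is not the same test for everyone. Extra readings can add high values but cannot remove any. Two patients with the same glucose control could therefore be classified differently because one tested after both meals. No readable text says which readings count, so two sites could also treat the same diary differently. The fasting condition has the same form, but the card has one fasting field a day, so its denominator on the card stays at seven.

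At stake is misclassification in the only primary endpoint of a trial of about 100 patients, with a planned power of 90% and little to spare. If the extra failures fell equally on successes in both arms, the treatment difference would shrink.

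**Working it through.** **The plan's own figure.** Protocol 9.1 gives 44 per arm for 23% vs 55%, 90% power, two-sided 0.05. With unpooled variance, n = (1.960 + 1.282)² × (0.23×0.77 + 0.55×0.45) / 0.32² = 10.51 × 0.4246 / 0.1024 = 43.6, so 44. Exact power of the Pearson test at 44 per arm is 88.8%, inside the stated 87% to 90%. The plan is sound on its own terms.

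**The range of tolerance.** The minimum is 7 × 1 = 7 readings and the card's capacity is 7 × 2 = 14. The allowed shares are 4/7 = 57.1% and 4/14 = 28.6%.

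**Chance of failing this condition.** Let q be the chance that one reading is high. The documents do not give it, so a range is assumed. The failure probability is P(X ≥ 5), binomial for independent readings and beta-binomial for a within-patient correlation of 0.2.

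| q | Independent, 7 vs 14 | Correlation 0.2, 7 vs 14 |
|---|---|---|
| 10% | 0.02% vs 0.9% | 1.7% vs 9.6% |
| 20% | 0.5% vs 13.0% | 5.5% vs 24.0% |
| 30% | 2.9% vs 41.6% | 11.9% vs 41.0% |

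The direction needs no assumption. The size does.

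**Power if both arms have the same q.** Extra failures = share of patients giving 14 readings × (P14 − P7). The Cochran-Mantel-Haenszel test was simulated with 50 per arm in strata of 17/21/12 (34/42/24% of 50), success rates of 13/23/55% vs 40/55/84%, and one-sided 0.025. Those rates are assumed to hold under seven readings, which gives a baseline of 90.2%. Both arms' rates are then multiplied by (1 − extra).

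| q, share giving 14 | Independent | Correlation 0.2 |
|---|---|---|
| 10%, a quarter | 90% | 89% |
| 10%, all | 90% | 85% |
| 20%, a quarter | 88% | 87% |
| 20%, half | 86% | 84% |
| 30%, half | 76% | 80% |

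**Power if reparixin lowers post-prandial readings.** A common factor presumes that the drug leaves post-prandial glucose untouched, although post-prandial control is part of what the endpoint measures. Using a separate q for each arm, with half the patients giving 14 readings:

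| q placebo / reparixin | Independent | Correlation 0.2 |
|---|---|---|
| 20% / 10% | 93% | 91% |
| 30% / 10% | 97% | 93% |
| 30% / 20% | 94% | 88% |

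The middle stratum shows why the sign changes. At 20% / 10% with independent readings, the extra failures are 0.5 × (0.1298 − 0.0047) = 0.0626 on placebo and 0.5 × (0.0092 − 0.0002) = 0.0045 on reparixin. The rates become 0.23 × 0.9374 = 21.6% and 0.55 × 0.9955 = 54.8%, a gap of 33.2 points against the planned 32. With 0.0626 applied to both arms, the gap is 0.32 × 0.9374 = 30.0 points.

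**What a one-reading-per-day rule would cost.** It needs a value on all seven days. If each day has an independent chance d of holding one, the share of patients with an incomplete week is 1 − d⁷: 13% at d = 0.98, 30% at 0.95 and 52% at 0.90 (d assumed). Those patients would have to keep the site's status or count as failures.

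**The case for a change.** The best case for a change is that it looks cheap. The criterion names one daily measurement as its basis, the diary is already in the database, and one sentence fixed before unblinding could select one after-meal value per day. That would put patients with a complete diary week on the same denominator and leave the limit of four untouched, in a trial with little power to give away.

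Part of this stands. The unequal tolerance is real, no readable text says which readings count, and the addendum's fingerstick-free definition is exploratory, so it does not alter the primary one.

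The remedy is less clean than it looks:

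- The wording sets a minimum, so it expressly allows more than one reading a day. A selection rule would set aside high values that were actually observed.
- It would override the status assigned at the site. With the site's status as fallback, the primary endpoint would follow two rules, split by diary completeness, which arises after randomization.
- Taking the first value of the day means lunch for some patients and dinner for others, a new inequality.
- It would change how a protocol endpoint is counted through the SAP alone, while SAP 1.2 declares no changes from the protocol.

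**Conclusion.** No change follows. An absolute weekly cap with a floor on testing is a coherent criterion: it is simple for sites to apply, and more testing finds more true excursions. Its price is a tolerance that runs from 57% to 29% of readings according to how much a patient records. Only patients who meet every other condition and record more than the minimum are affected.

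Under blinding, with allocation balanced within centres, recording habits should be alike in the two arms, so no bias and no type I error inflation is expected. That would fail only if recording differed by arm, and nothing in the documents suggests it.

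No power loss can be attributed to the criterion. The results above run from about 76% to 97% around a 90% baseline, and they depend on three things the documents do not give: the rate of high readings, the share of patients recording both meals, and whether reparixin lowers post-prandial glucose. The baseline is itself an assumption. The planning rates come from a retrospective series whose counting rule is not stated; if they already reflect the recording that occurs in this trial, the loss is zero.

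The missing statement of which readings count is a gap that sites fill when they review the diary, and the SAP analyzes the status they record. Listing the diary data, as the SAP already plans, lets a reader see how many readings lie behind each classification. The difference between a 2-hour value in the definition and a value within 2 hours in Protocol 7.2 and on the card is a separate wording mismatch. Those passages should be reconciled, but this does not bear on the conclusion here.
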